8.3 Safety Variables

For all Parts of the study, safety and tolerability assessments will include adverse events, laboratory abnormalities, ECGs, and vital sign measurements.

9 ANALYSES

Table, figures and listing titles are denoted in underlined text.

9.1 General Analyses

Generally, summary statistics including N, mean, median, standard deviation, Q1, Q3, Min, and max will be generated for continuous variables. For the ordinal data such as OHSA scales, it will be treated as continuous variable for summary statistics. For categorical variables, count and % will be summarized.

Figures including serial plot, box plot, bar chart, and heatmap will be employed to depict the data. For the longitudinal data, such as vital signs, blood pressures in seated, supine, and standing positions, OHSA scales, lab data, etc., serial pot or box plot will be generated to describe the changes. Bar chart will be used to depict the changes in scales of categorical data, e.g. OHSA scales. Heatmap will be used to depict the changes in blood pressure by

individual patient, with x-dimension as visit (study days), y-dimension as time points, and the colored heatmap to represent the categories of changes from baseline.

9.1.1 Subject Disposition

Subject disposition information will be summarized for all subjects by study Part (A and C) and by dose. Summaries will include:

- Number of subjects enrolled in Part A
- Number of subjects enrolled in Part C
- Number and percentage of subjects treated with study drug (Part C)
- Number and percentage of subjects completing the study (Part C)
- Number and percentage of subjects by reason discontinuing the study drug (Part C)
- Number and percentage of subjects by reason discontinuing the study (Part C)

For Part C, the subject disposition table will include the number (%) of subjects who were rolled over from Part A into the open-label extension study.

A listing of subject disposition will include the ITT analysis set status, the date of informed consent signed, the date of first dose and last dose of study drug, primary reason for subject discontinuation of study medication, the date of last visit, study completion status, and primary reason for study termination.

9.1.2 Demographics and Baseline Characteristics

Demographics including age, sex, race, ethnicity, height, weight, and BMI will be summarized for the ITT analysis set.

The following baseline characteristics data will be summarized descriptively:

- Underlying diagnosis of nOH (MSA, PAF, Parkinson's disease)
- Symptomatic (yes or no)
- OHSA question 1 at baseline

In addition, the following baseline characteristics will also be summarized descriptively for Part C:

- OHSA composite score at baseline
- OHDAS composite score at baseline
- OHQ composite score at baseline
- Orthostatic hypotension (yes or no) at baseline
- Duration of Standing at baseline
- · SBP (Seated, Supine, Standing) at baseline

A listing will be provided.

9.2 Efficacy Analyses

For all efficacy data analyses, the ITT group will be used unless otherwise specified.

9.2.1 Primary Efficacy Evaluation

For Part C, the primary endpoint is the improvement from baseline in the Likert scale "dizziness, lightheadedness, feeling faint, or feeling like you might black out" (OHSA, question 1) at week 4. The scales will be treated as continuous variable, and a summary table including descriptive statistics will be generated. A responder in Part C is defined as a subject who demonstrates at least a 2 unit decrease (improvement) from baseline in the OHSA question 1 at week 4. The proportion of subject who demonstrate \geq 1 unit, \geq 2 units, \geq 3 units, \geq 4 units improvement, no change, and worsen (by 1 and >1 unit) at each visit will be calculated with exact 90% confidence intervals and summarized by visit and dose level per each visit. In addition, OHSA question 1 improvement will be summarized by baseline value categories (baseline OHSA #1 \geq 2).

The example SAS code for summary of proportion of responders is following:

```
proc freq data = xxx;

by timepoint cat;

tables yes_no / binomial(exact) alpha=.1 cl;

ods output BinomialCLs = result_1;

run;
```

Where 'timepoint' is the time points for the measurements, 'cat' is the category of improvement (or no change, worsen) by number of unit, and 'yes_no' is the indicator for subjects in each category.

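### The example PROC FREQ code in SAP 9.2.1 names no response level and gives no coding for `yes_no`, so it can return the non-responder proportion, and it prints 100% for any cell with nobody in the category

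*SAP*

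**What the plan says.** SAP 9.2.1 defines a Part C responder as a subject with "at least a 2 unit decrease (improvement) from baseline in the OHSA question 1 at week 4". It asks for the proportion of subjects at each degree of improvement (at least 1, 2, 3 or 4 units), with no change, and with worsening (by 1 unit and by more than 1). These are to be "calculated with exact 90% confidence intervals and summarized by visit and dose level per each visit".

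The section then gives code, introduced by "The example SAS code for summary of proportion of responders is following". Its working parts are:

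- "proc freq data = xxx", with no ORDER= option;
- "by timepoint cat", so each time point and improvement category is analysed separately;
- "tables yes_no / binomial(exact) alpha=.1 cl", with no LEVEL= option.

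Only the BinomialCLs table is kept. The analysed variable is explained in one clause: "yes_no' is the indicator for subjects in each category". Neither document gives its codes, a format or a sort order. SAP 6.8 names SAS 9.3 or later as the software.

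**The concern.** For a one-way table, the BINOMIAL option reports the proportion of the first level in table order, which by default is the lowest unformatted value. With the usual codings of a yes/no indicator, that level is the negative one. The code would then deliver the proportion and limits for subjects who did not reach the stated improvement.

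A second problem does not depend on the coding. When everyone in a BY cell has the same value, only one level exists and its proportion is 100%, whichever level it is. A cell with no responders and a cell with only responders give identical output, so subtracting every printed value from 1 afterwards cannot repair the table.

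The code serves the responder summary attached to the primary endpoint. SAP 9.2.4 says that only descriptive summaries are provided, so a reader of the responder tables has the estimates and their intervals and no test alongside them.

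**Working it through.** **Inputs from the SAP.** Confidence level 90% in the text of 9.2.1; `alpha=.1` in the code; BY variables `timepoint` and `cat`; no LEVEL= or ORDER= option; coding of `yes_no` not given.

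**Assumptions.** The Part C sample size is not visible (SAP section 4), so all cell sizes and response rates below are illustrations. The default rule for the reported level is knowledge of the software and is not in the documents. SAS was not run; the rule was applied by hand.

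**Stated figure.** 1 − 0.10 = 0.90. The code's alpha agrees with the 90% in the text.

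**Interval formula (Clopper-Pearson, x of n, alpha = 0.10).** Lower limit = beta quantile at 0.05 with parameters (x, n − x + 1), or 0 if x = 0. Upper limit = beta quantile at 0.95 with parameters (x + 1, n − x), or 1 if x = n.

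**Mixed cells under 0/1, N/Y or No/Yes coding.** The first level is the negative one, so n − x replaces x.

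| Responders | Intended | Output of the example code |
|---|---|---|
| 18 of 30 | 60% (43.4% to 75.0%) | 12/30 = 40% (25.0% to 56.6%) |
| 6 of 20 | 30% (14.0% to 50.8%) | 14/20 = 70% (49.2% to 86.0%) |
| 14 of 20 | 70% (49.2% to 86.0%) | 6/20 = 30% (14.0% to 50.8%) |

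The output is the exact complement: the limits are 1 minus the intended upper limit and 1 minus the intended lower limit. If the responder level sorts first (for example 1 = Yes, 2 = No), mixed cells are correct.

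**One-level cells under any coding.** With x = 0 the only level present is the negative one, and with x = n only the positive one. Both print 100% with lower limit 0.05^(1/n).

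| Cell | Intended | Output of the example code |
|---|---|---|
| 0 of 5 | 0% (0% to 45.1%) | 100% (54.9% to 100%) |
| 5 of 5 | 100% (54.9% to 100%) | 100% (54.9% to 100%) |
| 0 of 20 | 0% (0% to 13.9%) | 100% (86.1% to 100%) |
| 20 of 20 | 100% (86.1% to 100%) | 100% (86.1% to 100%) |

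For n = 5, 0.05^(1/5) = 0.549 and 1 − 0.549 = 0.451.

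**How often.** With a true rate p for the category, an empty cell has probability (1 − p)^n. At p = 0.1 this is 0.9^5 = 59% for n = 5, 0.9^10 = 35% for n = 10 and 0.9^20 = 12% for n = 20. Such a rate is plausible for the rarer categories, such as worsening by more than 1 unit.

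**Which cells change meaning relative to the mixed cells.** Under 0/1 coding, mixed cells and empty cells both report the negative level. Only the all-responder cell reports the positive one, with probability p^n: at n = 4 and p = 0.5, 0.5^4 = 6.25%; at p = 0.3, 0.3^4 = 0.8%. If the responder level sorts first, the empty cell is the one that changes meaning.

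**The case against.** The code is a schematic. It is introduced as an example and has a placeholder data set, so it cannot be run literally. The governing prose asks for the right quantity, and nothing in the SAP proposes to report non-responders. The main summary of the primary endpoint treats the OHSA question 1 score as continuous and does not use this code.

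Reversal in mixed cells would also be conspicuous. The improvement categories are nested, so true proportions cannot rise from at least 1 unit to at least 4 units, while reversed ones cannot fall. SAP Appendix 1 shows a count beside each percentage, and Appendix 2 plans change summaries, bar plots, individual plots and an OHSA listing from the same data.

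All of this stands and limits the severity. It does not remove the defect. One-level cells are harder to notice, and they go wrong under every coding.

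Two stronger readings are tempting. A reader might infer that the small visit-by-dose cells come directly from this code. They do not: the BY statement has time point and category only, so each cell pools all subjects at that visit. Dose enters through the prose and the by-dose and subgroup responder tables in Appendix 2, for which the code would need extending. A reader might also add the two one-level probabilities at n = 4 and p = 0.5 and say that the meaning flips in 12.5% of cells. Under 0/1 coding the empty cell has the same meaning as the mixed cells, so the figure is 6.25%, and in that all-responder cell the printed 100% happens to be the correct responder rate.

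**Conclusion.** The point holds as a correction that should be made. As shown, the code returns the complement of the intended proportion if `yes_no` has any of the ordinary codings, and 100% for every empty cell under any coding. In the illustrations, 60% becomes 40% and 0 of 5 becomes 100%.

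A reader might infer that the trial's reported responder rates will be inverted. The documents do not support that: the coding is unstated, the code is labelled an example, the prose is correct, and planned counts and listings would expose a reversal. Nor does any visible decision rule depend on the responder interval.

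The conclusion rests on the SAS default for the reported level and, for the mixed cells only, on the negative level sorting first. All cell sizes and rates used are assumed.

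**What to change.** Revise the example in SAP 9.2.1 as follows:

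1. State the coding of `yes_no`.
2. Name the level: `binomial(exact level='1')`, or `level='Yes'` to match the coding.
3. Pre-aggregate to counts with an explicit zero row for each absent level, and use `WEIGHT count / ZEROS` so that both levels exist in every BY cell. Naming the level is not enough by itself, because that level may be absent from a cell.
4. Add dose to the BY statement for the by-dose tables.
5. Add a programming check that the printed proportion times N equals the responder count in the same table.

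The cost is a few lines of code and a small pre-aggregation step. Trial conduct and data collection are unaffected.

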9.2.2 Secondary Efficacy Evaluation

For Part C, actual score and its change from baseline in composite OHSA, OHDAS, and OHQ will be generated descriptively by study visit. For Standing and Seated SBP, as well as duration of standing, the actual value (in minutes) and its change from baseline will also be summarized descriptively by time point (pre-breakfast, pre-lunch) and study visit. In addition, categorical shift (categories from 0 to 10 by 1 minute, and ≥ 10 minutes) of change from baseline for standing duration will also be summarized. For Standing SBP, number and percent of subjects with SBP > 80 mmHg by time point will also be analyzed.

For primary and secondary endpoints, graphic display of the data will be generated. Mean+/-SD line plot and boxplot will be used to depict the change over time point for vital signs and scores in OHSA, OHDAS and composite OHQ. Heatmap will be used to plot the individual change over time points on the data for vital signs (Seated, Standing, and Supine SBP and DBP). Bar chart will be used to depict the changes in scales of categorical data, e.g. OHSA scales, and in change subgroup for Seated SBP and Duration of Standing.

9.2.3 Other Efficacy Evaluation

The following efficacy endpoints will also be explored:

- Physician Global Assessment descriptive summary on actual score and change from baseline over time, and number (%) of subjects by level of score and study visit
- Subject Global Assessment descriptive summary on actual score and change from baseline over time, and number (%) of subjects by level of score and study visit
- Subject Satisfaction Survey number (%) of subjects by level of score and study visit
- Supine SBP descriptive summary on actual value and change from baseline by study visit

- Change from Seated SBP to Standing SBP, Change from Supine SBP to Standing SBP, Change from Supine to Seated SBP - descriptive summary on actual value and change from baseline by time point and visit
- 24 Hour Blood Pressure monitoring including number (%) of subjects with outliers in 24 Hours SBP, subject listing of 24 Hour BP monitoring

Additional graphic display of the following efficacy endpoints will be generated:

- Individual plots in subject's actual scales over time in OHSA question 1, composite scores in OHSA, OHDAS, and OHQ. Plots for both all subjects enrolled in Part C and only the Part C completers will be generated.
- Individual plots in subject's actual values by time point and visit in Seated SBP, Supine SBP, Standing SBP, Change from Seated SBP to Standing SBP, Change from Supine SBP to Standing SBP, Change from Supine to Seated SBP, and Duration of Standing. For Change from Seated SBP to Standing SBP and Duration of Standing, plots for both all subjects enrolled in Part C and only the Part C completers will be generated.
- Mean+/-SD (from descriptive summary) line plot and boxplot for actual values over time in Seated SBP, Supine SBP, and Standing SBP.
- Mean+/-SD (from descriptive summary) line plot and boxplot for change from baseline over time in Change from Supine SBP to Seated SBP.
- Mean+/-SD (from descriptive summary) line plot for the percent change from baseline over time - Duration of Standing.
- Bar chart for the percent change from baseline in Duration of Standing.
- Individual plots in 24 Hours Vital Signs Monitor in SBP, DBP, HR, and Mean Arterial Pressure

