- k. Blood collection for NE analysis will be collected on Day 1 (within 30 minutes before dosing) and upon return to the clinic on Day 29. Please refer to the central laboratory manual.

SCHEDULE OF STUDY ASSESSMENTS (CONTINUED)

- I. Clinician's/Subject's Global Impression and OHQ (OHSA and OHDAS components) to be administered during clinic visits by a trained clinician and recorded on standardized paper forms (See [Appendix 4](#)). In addition while at home, the Clinician's/Subject's Global Impression and OHQ will be completed by telephone with the study coordinator. On all visit days the OHQ and Global Impression assessments should be completed at least 4 hours after dosing (but no more than 7 hours) and before lunch. For the Day 155 and 169 assessments, the timing of the "postdose" questionnaires should be calculated based on the Day 1 dosing time.
- m. On the study visit days marked above, subjects will receive a dose of study medication in the morning after supine blood pressures and the orthostatic standing test has been completed. On non-study visit days the subjects should take their dose of study medication in the morning at approximately the same time of day. On study days where the subject is traveling to the clinic, the subject should take their dose of study medication at home before traveling to the clinic. Subjects will return to the clinic on the day of their final dose. Day 140 is the day of the last dose received at the end of 5 months (20 weeks).
- n. Subjects will complete the Subject Satisfaction Survey on Days -1, 15, 29 and 140 (or at the time of early discontinuation) using the appropriate questionnaire listed in [Appendix 5](#).
- o. Safety labs should be collected Day -2 or on Day -1.

Sequence of study procedures during study visits (with *hypothetical* times for illustration):

- 7:00 am -Wake up
- 7:30 am - supine blood pressure after 5 and 10 minutes resting at 30 degrees elevation and orthostatic standing test (where applicable)
- 8:00 am - Dose with TD-9855 and eat breakfast

After a minimum of 4 hours but no more than 7 hours after dosing and before lunch:

- 12:00 pm - supine blood pressure after 5 and 10 minutes resting at 30 degrees elevation and orthostatic standing test (where applicable)
- 12:30 pm - Clinician/subject impression and OH Questionnaires (OHDAS and OHSA)
- 12:45 pm - lunch

TABLE OF CONTENTS

	PAGE
PROTOCOL SYNOPSIS	2
SCHEDULE OF STUDY ASSESSMENTS	12
LIST OF ABBREVIATIONS AND DEFINITION OF TERMS	20

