6.3.22 Subject Satisfaction Survey

Subjects will complete the Subject Satisfaction Survey ([Appendix 5](#)) on Day -1, Day 15, Day 29 and at the time of end of study therapy (either Day 140 or at the time of early discontinue, as appropriate).

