Appendix 5: Subject Satisfaction Survey

Patient Satisfaction Questionnaire – Day -1 Questions

To be completed by the subject on Study Day -1

1. Please circle the number below that represents how satisfied you are *currently* with your ability to manage your orthostatic hypotension (OH) symptoms. Consider both how effectively you can manage your symptoms and any side effects resulting from the products you currently use.

Very

Dissatisfied w/ Current
OH Symptoms Management

Very

Satisfied w/ Current
OH Symptoms Management

1 2 3 4 5 6

Subject initials: _____

Date Completed: _____

Patient Satisfaction Questionnaire – Day 15 and Day 29 Questions

To be completed by the subject on Study Day 15 and Study Day 29

1. Thinking over the *past week*, please circle the number below that best indicates how satisfied you have been with the ability of the medication you are taking in this clinical trial to manage your orthostatic hypotension (OH) symptoms:

Very

Dissatisfied with
Trial Medication

Very

Satisfied with
Trial Medication

1 2 3 4 5 6

2. Thinking over the *past week*, which statement best describes your impression of *how well* the study medication worked? (check one)

- The study medication didn't seem to work for me at all.
- The study medication provided some relief of my orthostatic hypotension (OH), but not as much as I would like.
- The study medication worked very well.

3. Thinking over the *past week*, which statement best describes your impression of the *side effects* that you experienced from the study medication? (check one)

- I experienced no/minimal side effects.
- I experienced some side effects, but they were acceptable given the efficacy of the study medication.
- I experienced significant side effects.

4. Thinking about your responses to questions 2 and 3 above; please circle the number that represents how likely would you be to continue taking this medication if you were not currently enrolled in a clinical trial?

Very
Likely to **Discontinue**

Very
Likely to **Continue**

1 2 3 4 5 6

Subject initials: _____

Date Completed: _____

Patient Satisfaction Questionnaire – End of Therapy Visit Questions

To be completed by the subject at the end of study therapy (Study Day 140 or at the time of early discontinue, as applicable)

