1. Based on your *overall experience thus far* in this clinical trial, how likely do you think you would be to use the medication if it were offered to you by a physician after it is approved by the FDA? (check one)

- Extremely likely
- Somewhat likely
- Somewhat unlikely (answer Question 2)
- Extremely unlikely (answer Question 2)

2. Answer only if you responded “Somewhat unlikely” or “Extremely unlikely” to Question 1, otherwise leave this question blank.

We'd like to understand, based on your *overall experience thus far* in this clinical study, why you would be unlikely to use the medication. Listed below are three reasons why you might choose not to use the medication. For each reason, please circle the number below that reflects the importance of each reason in explaining why you are unlikely to use the medication.

	Not at all important in deciding not to use			Very important in deciding not to use		
Not effective enough	1	2	3	4	5	6
Side effects too bothersome	1	2	3	4	5	6
Assume that it would be too expensive	1	2	3	4	5	6

Subject initials: _____

Date Completed: _____

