6.3 Analysis Windows

All assessments will be summarized using analysis windows. The terminology of unscheduled will be applied to assessments that are outside an analysis window regardless, of the nominal label associated with the assessments in the EDC system.

All data (scheduled and unscheduled visits) will be presented in the subject listings; however, unless noted otherwise, only data from assessments within analysis windows will be included in the summaries, statistical analysis, and calculation of derived parameters.

In part C, the analysis window will be +/-3 days for the scheduled visits from Day 8 through Day 29, ±7 days for scheduled visits between Day 57 through Day 169 as defined below.

Nominal Day	Start (days)	Stop (days)
8	5	11
15	12	18

Nominal Day	Start (days)	Stop (days)
22	19	25
29	26	32
57	50	64
85	78	92
113	106	120
140	133	147
155	148	162
169	163	175

If the scheduled visit is outside of the analysis window, data will not be counted in the summary tables. In each part, the summary tables by the scheduled visit will only use data recorded for the scheduled visit. Data collected at the unscheduled visit will not be counted in the summary table, however will be included in the subject listings.

General Selection Process for Multiple Records in an Analysis Window

In general, if multiple, valid, non-missing observations exist at a visit or collection time point then records will be chosen based on the following:

- The record closest to the nominal time point in question, or,
- The later record if the two visits are equidistant from the time point, or,
- The average (arithmetic mean) if there is more than one record at the time point (generally applies to assessments done in triplicate).

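### The End of Therapy satisfaction questions are due at Day 140 or at early discontinuation, but the SAP's by-visit calendar windows keep forms dated before Day 133 out of the Day 140 summary

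*SAP*

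**What the plan says.** Protocol 6.3.22 schedules the survey on Days -1, 15 and 29 and at the end of study therapy, which it defines as "either Day 140 or at the time of early discontinue, as appropriate". Footnote n of Protocol Table 2 and the heading of the last form in Appendix 5 give the same timing. The final form is therefore triggered by an event and not by a calendar day.

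Appendix 5 contains three different forms. The End of Therapy form asks "how likely do you think you would be to use the medication if it were offered to you by a physician", with four verbal answer levels. Subjects who answer on the unlikely side then rate three reasons: efficacy, side effects and expense. The Day 15 and Day 29 form has other items. One of them, scored 1 to 6, asks "how likely would you be to continue taking this medication if you were not currently enrolled in a clinical trial".

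SAP 9.2.3 places the survey among the explored efficacy outcomes and describes the output as "Subject Satisfaction Survey number (%) of subjects by level of score and study visit".

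SAP 6.3 sets the scope: "All assessments will be summarized using analysis windows". Its table gives Day 140 the range Days 133 to 147 and has no row for early termination or end of therapy. An assessment outside every window is called unscheduled whatever its label in the database. The section adds: "If the scheduled visit is outside of the analysis window, data will not be counted in the summary tables". Such data go to the subject listings. SAP 6.4 gives no rule for missing survey answers beyond its general rule of no imputation.

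**The concern.** The form is collected at an event but tabulated by calendar. Whether a subject's answer reaches the Day 140 column depends on whether that subject was still on drug near Day 140, and staying on drug is closely tied to what the form measures. Question 2, on why a subject would not use the drug, matters most for subjects who stopped because of side effects or lack of effect. Those are the subjects the Day 140 column misses.

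Early stopping is foreseen. The protocol and the SAP both provide for discontinuing dosing when supine hypertension or other adverse events persist after a dose reduction, and SAP 9.1.1 tabulates reasons for stopping study drug. Part C is open-label with no concurrent control, so no comparison arm would reveal the selection. SAP section 1 says the study results will guide further development. A likelihood-of-use percentage read from the Day 140 column could be taken as the view of all treated subjects when it is not.

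**Working it through.** The plan states no figure for this item, so there is nothing to reproduce. The check maps possible form dates to the SAP 6.3 windows.

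**Inputs.** Windows before Day 140 (SAP 6.3): Day 8 = 5–11, Day 15 = 12–18, Day 22 = 19–25, Day 29 = 26–32, Day 57 = 50–64, Day 85 = 78–92, Day 113 = 106–120. Day 140 = 133–147. Last scheduled dose: Day 140 (Protocol Table 2, footnote m). For the count, the form is taken as completed on the day of stopping.

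**Days 1 to 132, before the Day 140 window opens**

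| Where the date falls | Days |
|---|---|
| No window: 1–4, 33–49, 65–77, 93–105, 121–132 | 4 + 17 + 13 + 13 + 12 = 59 |
| Day 8 or 22 window (no survey scheduled) | 7 + 7 = 14 |
| Day 57, 85 or 113 window (no survey scheduled) | 15 + 15 + 15 = 45 |
| Day 15 or 29 window (different form) | 7 + 7 = 14 |
| Day 140 window | 0 |

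The total is 59 + 14 + 45 + 14 = 132. In another visit's window: 14 + 45 + 14 = 73. In no window: 59/132 = 44.7%. After Day 32 it is 55 of 100 days. Days 133 to 139 add 7 early days that do fall in the Day 140 window.

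**Two readings of SAP 6.3**

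- *By recorded visit.* The section also restricts by-visit tables to records made for the scheduled visit. A form labelled Day 140 but dated before Day 133 is out of window. A form labelled early termination belongs to no visit in the window table. Either way it is not counted.
- *By date.* A form from one of the 59 days is not counted. A form from one of the 73 days goes under another visit.

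The readings differ on where the form ends up. They agree that it does not reach the Day 140 column.

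**Illustration only, on assumed values.** Let d be the proportion stopping before Day 133, c the proportion of completers answering likely, and s the proportion of early stoppers answering likely. Suppose every early stopper returns a form.

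- Day 140 column: c
- All collected forms: (1 − d)c + ds
- Difference: d(c − s)

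With c = 80% and s = 20%:

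| d | All forms | Day 140 column | Difference, points |
|---|---|---|---|
| 10% | 74% | 80% | 6 |
| 20% | 68% | 80% | 12 |
| 30% | 62% | 80% | 18 |
| 40% | 56% | 80% | 24 |
| 50% | 50% | 80% | 30 |

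With c still 80%, d from 20% to 50% and s from 10% to 40%, the all-forms figure runs from 0.5 × 80 + 0.5 × 10 = 45% to 0.8 × 80 + 0.2 × 40 = 72%. The difference is zero if s = c and changes sign if s > c.

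**The case against.** The strongest reply is that this is a gap in specification and not a determined result. SAP 6.3 applies unless noted otherwise. The survey table title in Appendix 2 lacks the by-visit wording of neighbouring titles, and SAP 6.8 refers to a mock shell document that is not available here and may handle the form sensibly. The three forms have different items, so a programmer would be unlikely to pool an early End of Therapy form with Day 15 or Day 29 answers. The survey is neither a primary nor a secondary endpoint, and no inference is planned.

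Part of this stands. Whether an early form is omitted or misfiled is unclear, and the low priority of the item is fair. But SAP 9.2.3 does say the tabulation is by study visit, neither 9.2.3 nor 6.3 makes an exception for the survey, and under both readings the early form misses the Day 140 column.

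Three stronger conclusions are tempting, and the documents support none of them:

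- *Acceptability is reported for completers only.* The Day 15 and Day 29 form covers satisfaction, perceived efficacy, side effects and willingness to continue. It is tabulated for everyone with an in-window form, including those who stop later. Only the End of Therapy questions are affected.
- *Early stoppers' answers appear nowhere.* SAP 6.1 and 6.3 commit to listing all scheduled and unscheduled data. Appendix 2 names no survey listing, but that is an inconsistency in the index and does not show that the data go unreported.
- *An upward bias of known size is established.* The documents give neither a stopping rate nor any survey answers. Calendar days are not subjects, and stopping need not be spread evenly over them.

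**Conclusion.** Wrong as written, low severity. Applied literally, SAP 6.3 and 9.2.3 give a Day 140 summary of the End of Therapy questions that excludes every form dated before Day 133. That summary describes essentially only subjects who stayed on drug. The small exception is a form dated Days 133 to 139, or one completed some days after stopping that happens to fall in the window.

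The direction rests on an assumption: the summary looks too favourable if early stoppers answer less favourably than completers. That is plausible but not shown. The size cannot be computed from the documents, and the percentages in the illustration show only how the difference would scale. The Day -1, 15 and 29 forms are not affected, and nothing here touches the primary or secondary endpoints.

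**What to change.** In SAP 9.2.3, summarize the End of Therapy form at one analysis time point, End of Therapy (Day 140 or early discontinuation), and state that it is exempt from the 6.3 windows. Include every collected form. Show the number of treated Part C subjects without a form, and split the results by completers and early discontinuers. SAP 9.2.3 already plans several plots for all Part C subjects and for completers, so the distinction is not new to the plan.

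Tabulate each of the three forms by its own items and response levels. Name a survey listing in Appendix 2, in line with the commitment in 6.1 and 6.3 to list all data.

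The cost is short SAP wording, one table time point and one listing, with no new data collection. The resulting figure may be less favourable than the Day 140 column alone.
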